## Synopsis

The use of monoclonal antibodies either alone or as part of chemoimmunotherapy in oncology, benign and malignant hematology is expanding. Each year, United States Food and Drug administration (FDA) approves new agents or expands the indications of already approved agents. Of the 17 therapeutic monoclonal antibodies approved in 2017, 50% of them are indicated for hematologic and oncologic condition. With increasing number of approved agents and expansion of indications of existing agents, therapeutic monoclonal antibodies have become one of the fastest growing areas in the management of benign and malignant hematologic condition. With advancement of recombinant technology, newer agents are either partially or fully humanized. Despite this, they still carry significant risk of immune and non-immune mediated adverse events. Most of the therapeutic monoclonal antibody related adverse events (MCAAE) are either anaphylaxis or standard infusion reactions.

The severity of reaction is variable, ranging from mild involvement of single organ to severe and life-threatening reactions requiring hospitalization or even resulting in death. In a majority of patients, re-initiation of infusion following resolution of symptoms with or without additional medical intervention is possible.

Even for mild infusion reactions, where re-initiation of infusion is possible, there is resultant delay in delivery of infusions, distress to patients, and additional utilization of health care resources.

Due to unpredictability of standard infusion reaction, efforts have been focused on premedication to decreasing the incidence and severity of infusion reaction. Most institutions have protocols using corticosteroid, acetaminophen and antihistamine as part of their premedication protocols. This has reduced but not eliminated standard infusion reactions. Most recently, mast cell stabilizers are being added to standard protocols to further reduce the incidence and severity of standard infusion reactions with variable anecdotal success without formal study. Of all the monoclonal antibodies, only Daratumumab has been evaluated using this strategy.

This study seeks to formally evaluate the efficacy of mast cell stabilizer Montelukast 10 mg (SINGULAIR, Merck & Co., Inc.) in decreasing the standard infusion reaction in patients receiving therapeutic monoclonal antibodies either alone or as part of chemoimmunotherapy in hematologic condition. To our knowledge, this is the first study to formally evaluate this strategy in the multiple monoclonal antibodies. The monoclonal antibodies to be studied include: Blinatumomab (BLINCYTO, Amgen Inc.), Daratumumab (DARZALEX, Janssen Biotech, Inc.), Elotuzumab (EMPLICIT, Bristol-Myers Squibb Company), Gemtuzumab (MYLOTARG, Pfizer Inc.), Obinutuzumab (GAZYVA, Genentech USA, Inc.), and Rituximab (RITUXAN, Genentech US); the most common monoclonal antibodies in hematology associated with high risk of monoclonal antibody associated infusion reaction.

## Hypothesis

We postulate that 10 mg of Montelukast, when given at least 1 hour prior to infusion monoclonal antibodies in addition to standard premedication, will lead to at least 50% decrease in incidence of monoclonal antibody associated Standard Infusion Reactions compared to historic data. It will also lead to shorter infusion time and decrease use of additional health care resources (ER, hospitalization and discontinuation of infusion) and hence better tolerability of infusions.

## **Background/Significance**

Immunoglobulin molecules (antibodies) are multifunctional components of immune system produced by B-lymphocytes to facilitate cellular and humoral reaction to host and foreign antigens. Most antibodies are produced, as part of immune response, by diverse clones of B-lymphocytes to antigens. They are polyclonal and target portions of antigens that induced their response. Immunoglobulins can also be monoclonal i.e. produced by single clone of B lymphocyte against a specific antigen.

Monoclonal antibodies are produced commercially using recombinant technologies; they have been available in clinical use since 1985. Since revision of naming convention of therapeutic monoclonal antibodies in 2017, over 500 monoclonal antibodies have been registered(1). In 2017 alone, 17 therapeutic monoclonal antibodies are approved by Food and Drug Administration (FDA), of which 8 are indicated for hematologic and oncologic malignancy(2).

In hematology and oncology, monoclonal antibodies are either used alone or in combination with conventional chemotherapy for management of various benign or malignant conditions. Despite high clinical benefit, their drawback has been their unpredictable adverse effects (infusion reactions). For this reason, newer generations of monoclonal antibodies are either partially or fully humanized. Despite this innovation, their use still carries variable risk of infusion reaction depending on the agent, clinical indication and clinicopathologic characteristic of individual being treated.

Monoclonal antibody associated infusion reactions are generally divided into four general types; type 1 like reaction (most common), cytokine- release syndrome, mixed reaction and type IV reaction (least common) (3). For practical purpose, the above are grouped into anaphylaxis infusion reactions (AIRs) and standard infusion reactions (SIRs).

AIRs are mediated by IgE and result in explosive reaction with initial or subsequent exposure. Re-challenge is generally not recommended.

SIRs are mediated by antigen and antibody interaction (human antihuman or human anti-chimeric) or cytokine released from mast cell and monocyte- macrophage systems. The rate and severity of this type can be mitigated by premedication.

The incidence rates of SIRs are highly variable ranging from 50-80% in Rituximab and Alemtuzumab to 20-30% in Trastuzumab and Cetuximab (4, 5). Incidence is highest with the first and probably the second doses but may recur with subsequent doses in up to 30%(6).

The severities of SIRs are also variable, ranging from mild involvement of single organ to severe reaction resulting in emergency room visit or hospitalization and death. In majority of patients with mild to moderate reactions, re-initiation of therapy with hours to days of break is possible.

Due to unpredictability of SIRs, efforts have been focused on decreasing the incidence and severity of infusion reaction with premedication. Most institutions have adopted various combinations of corticosteroid, acetaminophen and antihistamine as part of their premedication protocols with variable success in reducing the incidence and severity of SIRs.

Despite the above, SIRs still occur with high rates and severities resulting in treatment delays, infusion prolongations, need for additional doses of premedication, emergency room visits and

sometimes hospitalizations. These not only lead to increased cost of treatment but also lasting psychological impact of treatment of patients.

To mitigate the above, efforts are being directed at modifications of premedication or addition of newer agents to further reduce the incidence and severity of SIRs and hence improve tolerability.

Most recently, Montelukast, a mast cell stabilizer has been reported in multiple retrospective and observational studies to either decrease the incidence rate of infusion reactions, shorten infusion time and or decrease the use of additional doses of premedication like corticosteroids whose effect may be counterproductive (7). This has resulted in wide spread use of Montelukast as part of premedication of some monoclonal antibodies without formal study.

Our pilot study seeks to evaluate whether 10 mg of Montelukast, when given at least one hour prior to infusion of monoclonal antibodies with high risk of infusion reaction (Blinatumomab, Daratumumab, Elotuzumab, Gemtuzumab, Obinutuzumab, and Rituximab) will decrease the incidence and severity of infusion reactions, shorten infusion time and improve tolerability. It also seeks to evaluate the frequency of use of extra doses of premedication during the infusion, particularly, corticosteroid whose use is associated with toxicity and is counterproductive to treatment in some situation. This will help identify new regimens to reduce the incidence and severity of SIRs. Information obtained will be hypothesis generating for a future Phase 3 randomized trial with eventual goal of modification of standard of care of monoclonal antibody premedication.

## **Purpose of the Study**

### *Aim*

To evaluate the efficacy of 10 mg of Montelukast in reducing the incidence and severity of monoclonal antibody associated standard infusion reactions (SIRs).

### *Primary Objective*

To report the incidence of monoclonal antibody associated SIRs when 10 mg of Montelukast is added to standard premedication.

### *Secondary Objectives*

1. To report rate of use of extra doses of premedication during infusion of monoclonal antibodies in the cohort
2. To determine the average duration of infusion of above monoclonal antibodies in the cohort

## **Design of the Study:**

This is a Phase II, single arm, open label, clinical trial.

## **Sample Size:**

A total of 100 patients will be screened with anticipated enrollment of 80 into the study. This is based on resources and estimated patients' availability for the study.

## **Patient Population (Eligibility and Exclusion Criteria):**

Consecutive patients who are seen and treated for various hematologic or oncologic malignancies with monoclonal antibodies (Blinatumomab, Daratumumab, Elotuzumab, Gemtuzumab, Obinutuzumab, and Rituximab) in Community Medical Centers- CMC (Community Regional Medical Center (CRMC), and Clovis Community Medical Center (CCMC)) and affiliated Ambulatory Infusion Centers (East Medical Plaza AIC, Clovis Community AIC, and Community Cancer Institute AIC) will be approached for study enrollment. Patients will be recruited from CCI, CCMC, and CRMC when they present for evaluation for hematologic or oncologic malignancy by PI or one of the sub-I's. Only patients treated by PI or sub-I's will be recruited into the study. No additional patients from external referral from other hematologist, oncologist, or PCP will be recruited unless they are seen by PI or Sub-I's for treatment evaluation.

Potential subjects will be approached when they present for pre-chemotherapy evaluation for their first dose of chemoimmunotherapy or immunotherapy for above named therapeutic monoclonal antibodies. Subjects who express interest in the study will then be consented for screening, registration and enrollment.

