### *Eligibility Criteria*

1. Patients must be at least 18 years.
2. Able to provide consent for study participation (English and Spanish).
3. Patients with hematologic disorders or malignancies starting on any of the following monoclonal antibodies alone or in combination with chemotherapy (Blinatumomab, Daratumumab, Elotuzumab, Gemtuzumab, Obinutuzumab, and Rituximab).
4. Able to tolerate leukotriene antagonist including Montelukast.
5. Able to tolerate oral intake.
6. Available for follow up by phone and on site.

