## **Study Methods:**

### *Study design:*

This is a Phase II single arm open label study evaluating 10 mg Montelukast given at least 1 hour prior to infusion of monoclonal antibody in addition to standard premedication. Monoclonal antibodies being evaluated include those commonly used to treat hematologic and oncologic malignancies like (Blinatumomab, Daratumumab, Elotuzumab, Gemtuzumab, Obinutuzumab, and Rituximab).

The study will be introduced to patients who are undergoing treatment with above monoclonal antibody by principal investigator or sub-investigator during routine pre-initiation of immunotherapy or chemoimmunotherapy visits. Patients who are interested in hearing more about the study will be consented to participate in the study. Subjects will then be screened by study coordinator with the PI or Sub-I and those who meet inclusion/exclusion criteria will proceed on the study.

Drug for the study will be dispensed by one of the Research pharmacists affiliated to CCI during routine pretreatment evaluation for patient to take home. The study drug (Montelukast) will be purchased from commercial sources using the funds from the study sponsor. This is an investigator-initiated research with full funding from institutional pilot research grant from the Central California Faculty Medical Group (CCFMG). No additional internal or external funding will be utilized for this study.

Study subjects will be given 10 mg of Montelukast to be orally self-administered at least 1 hour prior to beginning of chemotherapy section. The administration of drug by patient will be verified and documented by inpatient or AIC nurse by history.

If the monoclonal antibody is given more than 3 times weekly, then patient will take Montelukast daily, including at least 1 hour prior to infusion or change of bag.

Standard premedication will be administered according to institution protocol. For details, see the flow chart below in appendix 1.

Rates, ratios and proportions with confidence intervals will be calculated for demographic characteristic and incidence of infusion reactions. McNemar's test will be used to test the differences of average incidence of infusion reaction between first and subsequent infusions.

*Intervention:*

Administration of Montelukast 10 mg at least 1 hour prior to initiation of up to 6 infusion doses/bag changes

*Control:*

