Historic literature and retrospective chart review of patient's treated with above therapeutic monoclonal antibodies from January 2014 to December 2019.

*Covariates:*

History hypersensitivity medications, history of Asthma or Atopy, history of CAD/COPD, Other chemotherapy received by patient during the infusion and tumor burden.

*Study Implementation:*

This study is completely voluntary, and enrolment will not affect the treating oncologist's decision or treatment plan. The study medication, Montelukast, is an FDA approved drug for other indications and is not known to pose serious risk to cancer patient undergoing monoclonal antibody or cancer chemotherapy. Patients will be monitored closely for potential drug-drug interactions during the study period.

Information obtained from patients during the study period will be used solely for study purposes. No additional tissues or samples will be obtained for study purpose other than what is collected or required by treating physician as part of standard of care.

Privacy and confidentiality of patients' information will be protected per CMC guidelines.

Participation of study by subject is voluntary and will not require additional visits other than 24-hour post infusion phone call to complete a study related questionnaire. Study subjects will not be reimbursed for participation.

Study will be conducted over 2 years with an estimated yearly accrual of at least 40 patients per year.

The study will be conducted upon approval of CMC Institutional Review Board IRB and will follow Helsinki declaration and Good Clinical Guideline.

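### The chart-review control has no stated selection or index-infusion rule to match the trial's first-dose entry, so the 50% comparison with historic data may be biased in either direction

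*Combined protocol and SAP*

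**What the plan says.** The Hypothesis is comparative: at least a 50% decrease in standard infusion reactions (SIRs) against historic data.

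Trial cohort:
- Patient Population: "Only patients treated by PI or sub-I's will be recruited into the study". They are approached at the visit before "their first dose of chemoimmunotherapy or immunotherapy for above named therapeutic monoclonal antibodies".
- Eligibility Criteria, item 3: "Patients with hematologic disorders or malignancies starting on any of the following monoclonal antibodies alone or in combination with chemotherapy".
- Exclusion Criteria: item 1 removes patients given these antibodies for other indications. Item 3 removes patients already taking montelukast or another leukotriene antagonist for another reason.
- Intervention and Data Collection: each patient is followed for up to six infusions or bag changes.

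Control cohort:
- Study Methods, Control: "Historic literature and retrospective chart review of patient's treated with above therapeutic monoclonal antibodies from January 2014 to December 2019". The Confidentiality and Privacy section adds only that the retrospective data come from the electronic record.

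Risk by dose number, from Background/Significance: "Incidence is highest with the first and probably the second doses but may recur with subsequent doses in up to 30" percent.

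The Covariates paragraph lists hypersensitivity history, asthma or atopy, CAD/COPD, concurrent chemotherapy and tumor burden. Prior exposure to the same antibody is not on it. Statistical Analysis describes no comparison with the control and no adjustment.

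**The concern.** A historic control is useful only if its patients would have had the same reaction rate as the trial patients without montelukast. Here the trial's entry point is fixed and the control's is not. On the Control paragraph as it stands, the chart review could count reactions at any infusion number, in a first or a repeat course, for any indication, and in patients who received montelukast. The last is a practical possibility, because Background/Significance reports that montelukast is already widely used as premedication for some of these antibodies.

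The protocol itself says that risk depends on dose number. If one cohort holds more lower-risk infusions than the other, the ratio of the two rates moves for reasons unrelated to montelukast. There is a smaller gap on the trial side. Starting an antibody at a first dose does not rule out exposure in an earlier course, and no criterion or covariate captures it.

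At stake is how to read the 50% figure, which is meant to inform a later randomized trial. A control with no written selection rule can also be assembled after the trial results are known.

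**Working it through.** **Plan's own figure.** The enrolment of 80 equals 2 years × 40 per year, and Sample Size says it rests on resources and availability. It uses no control rate, so there is no power calculation to reproduce. What follows illustrates the mechanism and does not estimate the bias.

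**Inputs**
- p1, rate at a first infusion: 60% assumed, varied from 50% to 80%. Background/Significance gives 50-80% for rituximab and alemtuzumab. Only rituximab is a study antibody, and the other five have no rate there.
- p2, rate in lower-risk infusions: 30%, the upper figure in Background/Significance for subsequent doses. It fits a control that mixes in later infusions. Applying it to re-treated patients at the start of a new course is a further assumption.
- w, share of lower-risk infusions or patients in a cohort: not in the documents. Values of 20%, 30% and 50% are assumed.

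**Formula.** Mixed rate h = p1 × (1 − w) + p2 × w.

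**Case A: only the control is mixed, and montelukast truly halves the rate.** Apparent reduction = 1 − (p1/2)/h.
- p1 = 60%, w = 20%: h = 0.48 + 0.06 = 0.54; 1 − 0.30/0.54 = 44.4%.
- p1 = 60%, w = 30%: h = 0.42 + 0.09 = 0.51; 1 − 0.30/0.51 = 41.2%.
- p1 = 50%, w = 50%: h = 0.25 + 0.15 = 0.40; 1 − 0.25/0.40 = 37.5%.
- p1 = 80%, w = 50%: h = 0.40 + 0.15 = 0.55; 1 − 0.40/0.55 = 27.3%.

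The benefit is understated.

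**Case B: only the trial is mixed, and montelukast does nothing.** Apparent reduction = 1 − h/p1.
- p1 = 60%, w = 20%: 1 − 0.54/0.60 = 10%.
- p1 = 50%, w = 50%: 1 − 0.40/0.50 = 20%.
- p1 = 80%, w = 50%: 1 − 0.55/0.80 = 31%.

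A benefit appears where there is none. This could arise from re-treated patients in the trial, or from setting a trial rate pooled over six infusions against a first-infusion historic rate.

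**Case C: both cohorts have the same mix.** With p1 = 60%, w = 20% in each and a uniform halving, the control rate is 54% and the trial rate 27%; 1 − 0.27/0.54 = 50%. There is no bias.

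The error therefore depends on the difference in mix between the cohorts. The documents give the mix for neither.

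**The case against.** Several points on the other side are sound.

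- A reader might infer that the chart review takes anyone treated and that the cohorts do differ. The Control paragraph is one line and states no rule either way. It could still be carried out on first doses only. The documents support no more than that the cohorts may differ.
- A reader might also infer that the trial admits patients in mid-treatment, from "The study will be introduced to patients who are undergoing treatment with above monoclonal antibody". The rest of that sentence places the approach at visits before treatment starts, which agrees with Patient Population and Eligibility Criteria. The trial does set entry at a first dose, and the only gap is exposure in an earlier course.
- The restriction to the investigators' own patients might be read as a source of different risk. Nothing supports that. Premedication follows institution protocol and infusions follow standard of care, and neither is described as varying by clinician.
- The illustration borrows a later-dose figure and assumes the shares. Case C shows that the bias vanishes if the mixes are equal.
- The primary objective and endpoint are descriptive, Statistical Analysis has no test against the control, and the study calls itself a hypothesis-generating pilot. This limits the weight of the point. It does not remove it, because the Hypothesis and the Control paragraph still commit to the historic comparison.
- The data-collection appendix is not in the text available for this review, so prior exposure may already be recorded.

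**Conclusion.** The concern holds in a limited form. The plan does not show that the chart-review control and the trial cohort are comparable in infusion number, indication, montelukast use or prior exposure, although its own background says that risk varies by dose number. The comparison with historic data may therefore be biased, and it cannot be assumed to be conservative.

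Under the stated assumptions, a true halving reads as 27% to 44% when only the control is mixed. A reduction of 10% to 31% appears with no drug effect when only the trial is mixed. These figures depend on assumed shares and on a 30% rate that describes later doses. They show that the error could matter, not how large it is.

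The descriptive estimate of SIR incidence in the trial is not invalidated. The change is worth making before the chart review is extracted.

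**What to change.** In the Control paragraph of Study Methods:
- Restrict the chart review to patients who meet the trial criteria that a chart can verify: age, indication, a listed antibody, the same sites, and no montelukast or other leukotriene antagonist, including as premedication. Criteria such as consent and telephone availability cannot sensibly be applied, and no match on treating clinician is needed.
- Index each control at the first infusion of the course and follow over the same span of up to six infusions or bag changes, so that rates are compared at the same infusion number.

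In the Covariates paragraph, add prior exposure to the same antibody in an earlier course, recorded in both cohorts.

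In Statistical Analysis, state that the historic comparison will be reported by prior exposure, or repeated as a sensitivity analysis in unexposed patients.

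The cost is a few sentences and at most one data field, with no added visits. The control cohort becomes smaller. The unexposed-only analysis also uses fewer than the planned 80 trial patients if any were previously exposed, and these are already spread over six antibodies.
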